The objective of this study is to assess the efficacy of a SHPB for pain relief following laparoscopic hysterectomy. The superior hypogastric plexus lies in the presacral space and supplies autonomic innervation to the central pelvis. This plexus is suspected to play a role in postoperative pain following a hysterectomy. We hypothesize that a SHPB using the anesthetic bupivacaine will reduce patients' pain scores and opioid consumption following a laparoscopic hysterectomy.

VIII. Trial design:

This study is designed as a multi-center, randomized, single-blind, controlled trial of patients scheduled for a laparoscopic hysterectomy. Patients will be randomized to two groups: one group will receive a SHPB and laparoscopic hysterectomy, and the other will receive no block and laparoscopic hysterectomy.

METHODS

IX. Study setting:

The study will be conducted at three sites: Brigham and Women's Hospital (BWH)/Brigham and Women's Faulkner Hospital(FH), University of North Carolina Medical Center (UNC) and George Washington University (GWU).

X. Eligibility criteria:

Patients over 18 years of age who are scheduled for a laparoscopic hysterectomy at participating sites will be recruited to participate. Patients of all comorbidities will be eligible for inclusion; specifically, patients with chronic pain syndromes will not be excluded so as to evaluate the efficacy of SHPB in this population. The exclusion criteria include patients who are unwilling to consent, who have an allergy to block medications used in the trial, are undergoing a sacrocervicopexy or a sacrocolpopexy, are undergoing a laparotomy, or those with anatomy that limits the safe application of a presacral injection (per the surgeon's discretion at the time of the procedure). Patients will not be excluded if they undergo other concomitant procedures during laparoscopic hysterectomy. While concomitant procedures may contribute to patients' pain following laparoscopic hysterectomy, this will improve the external validity of the trial. Moreover, randomization should balance differences in patients and procedures between the two treatment arms.

XI. Interventions:

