If the patient is randomized to a SHPB, it will be performed laparoscopically by the gynecologic surgeon at the start of the hysterectomy procedure. The SHPB block will contain 10 mL of 0.25% bupivacaine hydrochloride (2.5 mg/mL = 25 mg). The injection will be performed by tenting the presacral peritoneum, aspirating with a laparoscopic needle-tip syringe to ensure extravascular placement, and injecting the block with the laparoscopic needle-tip syringe (Appendix XXXIV). Patients in the control arm will undergo the planned procedure with no intervention. Following the procedure and intervention, surgeons will be

asked to complete a worksheet to assess the feasibility and safety of presacral injection, as well as details regarding the procedure (Appendix “SHPB MD Worksheet”).

All participants will undergo a surgically-indicated laparoscopic hysterectomy as planned. As per routine practice, all patients will also receive an incisional anesthetic using 20 mL of 0.25% bupivacaine at the laparoscopic port sites. Patients in the intervention group will additionally undergo a SHPB (10 mL of 0.25% bupivacaine laparoscopically injected in the presacral space) at the start of the procedure. The surgical risks of a SHPB are similar to any surgical procedure and include bleeding, infection, and injury to surrounding vessels and organs. These risks are expected to be very rare as all participating surgeons are expert laparoscopists who have safely operated in the presacral space. Viewing a video demonstrating this technique will also be required of all participating surgeons prior to the study. If a patient’s anatomy or pathology prohibits the safe application of a SHPB then the intervention will be abandoned.

All surgeons who will enroll patients from BWH, FH, UNC and GWU are experienced laparoscopic surgeons who have performed at least 100 advanced laparoscopic procedures including hysterectomy. Laparoscopic hysterectomy will be performed by the participating surgeons in the usual fashion, with inherent operator-dependent variation in technique. All participating surgeons will be required to view a video describing the technique of SHPB to ensure the procedure is performed similarly in all patients.

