Patients will be randomized to two treatment groups: one group will receive the SHPB, and the other will receive no block. Patients will be randomized after informed consent is confirmed on the day of surgery. Subjects will be randomized using urn randomization with a 1:1 allocation of treatment and placebo, stratified by the three sites (BWH/FH, UNC and GWU). Randomized allocation of the treatment arms will be concealed in sequentially-numbered, opaque, sealed envelopes. The randomization sequence and concealed allocation envelopes will be prepared by a research assistant and unknown to the remainder of the study staff. A placebo arm (e.g. presacral injection of saline) was not designated given little to no anticipated benefit of a sham block. For the treatment arm, the risks of presacral injection are anticipated to be very rare and superseded by the potential benefit of reduced postoperative pain as demonstrated in patients undergoing abdominal hysterectomy.¹⁰

XVII. Blinding:

Patients will be blinded to the treatment arm; however, the surgeon and operating room staff will know if a patient has been randomized to receive the block during the hysterectomy. Nurses in the recovery unit and on the inpatient floors will also be blinded to the treatment arm. The Medication Administration Record will document a blinded medication for patients in the trial to reduce the risk that staff caring for patients outside the operating room become aware of the treatment arms.

XVIII. Data collection methods:

Postoperative pain scores will be collected by a registered nurse upon admission to the recovery unit, and at every hour for four hours or until the patient is discharged. Most patients are discharged home on the same day as surgery with a recovery unit stay between two to six hours depending on the patient. If a patient is admitted to the hospital, the worksheet will be completed by the recovery unit nurse for as long as the patient is in the recovery unit and completed by the floor nurse for a total of four hours postoperatively. Pain scores will be

collected using the Visual Analog Scale to ask patients their pain level on a scale of 0 to 10, where 0 indicates no pain and 10 indicates the worst pain imaginable.

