All healthcare personnel involved in this study will be responsible for completing correct operative and postoperative data. Patients will be asked to complete a daily postoperative diary which they will return at their postoperative visit. All other data points will be abstracted from patient medical records by research assistants. A minimum number of persons will be involved with the data abstraction in an attempt to decrease introduction of bias. The research assistants will also keep a copy of all source documents such as informed consent on file. All data will be kept in password-protected computer systems, locked file cabinets, and offices accessible only to study staff.

XX. Statistical methods:

Statistical analysis will be performed to test the null hypothesis that there is no difference in VAS pain scores or opioid consumption following laparoscopic hysterectomy with and without a SHPB. The primary analysis will be intention to treat, i.e. those patients randomized to the two treatment arms regardless of the intervention or outcome assessment. The primary outcome (immediate postoperative VAS pain scores in the recovery unit for four hours) will

be treated as continuous as well as dichotomized variables and compared using Student's t-tests if continuous and normally distributed, Wilcoxon tests if continuous and non-normally distributed, and Chi-square tests if dichotomized. A linear regression will be performed to adjust for the two participating sites. As patients are randomized to the two treatment groups, no additional adjustment for potential confounding variables is anticipated to be necessary. Subgroup analyses will be performed on patients undergoing a hysterectomy for pelvic pain and patients who undergo a laparoscopic hysterectomy without concomitant procedures. The final analysis will be conducted at the 0.05 level of significance and the interim analysis will be conducted at the 0.002 level of significance (to minimize type I error). Statistical analysis will be performed using appropriate statistical software and with the assistance of a biostatistician.

XXI. Data monitoring:

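### The two subgroup analyses have no interaction estimate, and one subgroup is defined by what was done after randomization

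*Combined protocol and SAP*

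**What the plan says.** Section XX (Statistical methods) says: "Subgroup analyses will be performed on patients undergoing a hysterectomy for pelvic pain". It adds a second population, "patients who undergo a laparoscopic hysterectomy without concomitant procedures". Section XII (Outcomes) names the same two.

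Section XX lists t, Wilcoxon and chi-square tests for the primary outcome, a linear regression that adjusts for site, and a 0.05 level for the final analysis. Beyond site, it says that "no additional adjustment for potential confounding variables is anticipated to be necessary". It gives no interaction term, subgroup test, subgroup size, multiplicity rule or exploratory label, and none appears elsewhere.

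Four other statements bear on the second subgroup:
- Section X (Eligibility criteria): "Patients will not be excluded if they undergo other concomitant procedures during laparoscopic hysterectomy".
- Section XVI (Assignment of interventions): randomization takes place on the day of surgery and is stratified by site only.
- Section XI (Interventions), on the block: "it will be performed laparoscopically by the gynecologic surgeon at the start of the hysterectomy procedure".
- Section XVII (Blinding): "the surgeon and operating room staff will know if a patient has been randomized to receive the block during the hysterectomy".

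**The concern.** There are two separate problems.

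**No comparison of effects.** A p-value computed inside one subgroup addresses whether the block works there. It does not address whether it works better or worse there than in other patients; that needs the difference between the two effects. Without it, a significant result in pelvic-pain patients, or a non-significant result in hysterectomy-only patients, invites a claim of differential efficacy that the analysis cannot support.

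**A subgroup fixed after randomization.** Membership of the hysterectomy-only group depends on what was done in theatre. The surgeon knows the arm from the start of the operation, before any later decision to add a procedure. If such decisions differ by arm, the two arms within that subgroup are no longer comparable by design. Section X relies on randomization to balance procedures, but randomization protects only what is settled before allocation. This is possible selection bias, distinct from chance findings. It does not touch the pelvic-pain subgroup, because the indication for surgery is a baseline factor.

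**Working it through.** **Inputs from the documents (section XIV).** Planning rates for a VAS score below 4 at two hours: 63% and 25%, a difference of 0.38. Alpha 0.05, power 80%, 10% loss. Stated requirement 58; recruitment target 100, 50 per arm.

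**Assumptions.** Subgroup shares are not given, so f = 20% to 50% is assumed. Tests are two-sided, membership is balanced between arms, and the calculation uses all 100 patients.

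**Step 1: the plan's own figure.** With mean rate 0.44:
- Null term: √(2 × 0.44 × 0.56) = 0.702.
- Alternative term: √(0.63 × 0.37 + 0.25 × 0.75) = 0.6485.
- n per arm = [(1.96 × 0.702 + 0.842 × 0.6485) / 0.38]² = 25.6, so 26 per arm and 52 in total.
- 52 / 0.9 = 57.8, so 58. The stated figure reproduces.

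**Step 2: power at the recruitment target.** Power = Φ[(0.38√n − 1.96 × 0.702) / 0.6485]. At n = 50 per arm this is 97.8%; at 45 per arm, 96.5%.

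**Step 3: power inside a subgroup, and disagreement with its complement.** The same formula applies with 50f and 50(1 − f) per arm. Disagreement = a(1 − b) + b(1 − a), where a and b are the two powers and the true effect is the same 38 points in both.

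| Share f | Power in subgroup (a) | Power in complement (b) | Disagree | Only subgroup significant |
|---|---|---|---|---|
| 20% | 0.394 | 0.943 | 0.594 | 0.022 |
| 30% | 0.559 | 0.911 | 0.452 | 0.050 |
| 40% | 0.691 | 0.862 | 0.362 | 0.096 |
| 50% | 0.790 | 0.790 | 0.331 | 0.166 |

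**Step 4: a smaller true effect.** Suppose that the effect gives only 80% power overall, so that the expected overall z is 1.96 + 0.84 = 2.80. The expected z values are then 2.80√f and 2.80√(1 − f). At f = 20% they are 1.25 and 2.50, the powers are 0.24 and 0.71, and disagreement is 0.61. At f = 50% both powers are 0.51 and disagreement is 0.50. The ranges are 24% to 51% for power and 50% to 61% for disagreement.

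**Step 5: no block effect at all.** Take shares of 30% and 50% with independent membership. The two subgroup z-scores then have correlation √(0.3 × 0.5) = 0.39. At least one is significant 9.3% of the time, and 7.0% of the time while the overall test is not significant. A simulation with t-tests in 100 patients (20,000 runs, three pairs of shares) gives 9.0% to 9.6%. Two independent tests would give 1 − 0.95² = 9.75%.

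**Step 6: precision of the interaction.** With equal variance, its standard error divided by that of the main effect is 1 / √(f(1 − f)): 2.5 at 20%, 2.18 at 30%, 2.04 at 40% and 2.0 at 50%. If the whole 38-point effect lay in the subgroup and none outside it, interaction power would be about 39% to 57%. The smallest difference in effects detectable with 80% power is about 51 to 64 percentage points.

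**Step 7: order of events for the second subgroup.** Consent, then randomization, then surgery with the block at the start, then any further intraoperative decision by the unblinded surgeon. The surgeon's worksheet is completed after the procedure, and procedure type is collected (sections XI and XVIII). Nothing in the text requires the planned procedure to be recorded before randomization.

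**The case against.** The plan names two populations and no complements, and it makes no claim that the block works better in one group than another. Section X keeps patients with chronic pain in order to learn about efficacy in them, which is a question within a population. The disagreement figures need a complement test that nobody has planned. This stands, and those figures are conditional for that reason. The lack of an interaction estimate remains, because anyone comparing a subgroup with the rest of the trial has nothing else to use.

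A reader might also infer that each subgroup will be tested at 0.05. Section XX does not say so: it names no subgroup test and attaches 0.05 to the final analysis as a whole. Separate tests are the natural reading, not a stated rule.

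The disagreement figure mixes two directions. At a 20% share, 57 of the 59 points are the small subgroup missing significance while the complement reaches it. That is mostly a risk of wrongly concluding that the block fails in the subgroup.

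A reader might infer that the unblinded surgeon will distort the second subgroup, or turn chance differences into apparent efficacy. The documents do not support either. They give no reason why a presacral injection would change which procedures are added, and section XI has patients undergo the operation as planned. Many concomitant procedures may be settled beforehand. What stands is that the definition allows the bias and the plan has no safeguard against it.

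Finally, only two subgroups are named, both prespecified, and the interaction test has low power. Low power does not argue against reporting the interaction. It shows that this trial can support few subgroup claims, which the plan should say.

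**Conclusion.** The point holds in a limited form. No treatment-by-subgroup interaction is specified, and analyses inside each subgroup cannot show a different effect there. The hysterectomy-only subgroup conditions on events after randomization under a surgeon who knows the arm; the direction and size of any resulting bias are unknown.

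For assumed shares of 20% to 50% and the protocol's own rates at 100 patients, power inside a subgroup is about 39% to 79%, and disagreement with a tested complement is about 33% to 59% under identical effects. The less favourable ranges of 24% to 51% and 50% to 61% apply only if overall power were 80%. They should not be quoted as the trial's figures, because the planning rates give about 98%. The false-positive chance of about 9% for at least one subgroup also rests on assumed shares and on tests at 0.05.

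A reader might take this as a threat to the main result. It is not: the primary intention-to-treat comparison is unaffected, and only the interpretation of secondary analyses is at stake.

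**What to change.** In sections XII and XX:
1. Define the second subgroup by the procedure planned and recorded before randomization.
2. For each factor, report a treatment-by-subgroup interaction estimate with a 95% confidence interval from the site-adjusted model fitted to all randomized patients.
3. Show the effect in each subgroup with a confidence interval and make no separate significance claims.
4. Label both analyses exploratory.

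The cost is a few sentences and one extra data field for the planned procedure. If enrollment has begun, preoperative booking or consent records, where they exist, could supply it. The downside is an imprecise interaction estimate, with a standard error 2.0 to 2.5 times that of the main effect for shares of 20% to 50%, so few subgroup claims will be possible.
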